11.6 Fibrinogen inhibitory antibodies

Fibrinogen inhibitory antibodies are locally measured from sampling at screening, pre-dose (if applicable) and at the safety visit and will be categorized as positive, negative, or missing/not done.

Number of patients and percentages in each category will be summarized for part I (PK) and part II for SAF and on event level from part II for FBE. A listing with all patients fibrinogen inhibitory antibodies data will also be presented.

11.7 Viral safety

For part I viral safety is assessed based on pre-dose sample.

The following statistical analyses will be presented for part I pre-dose samples:

1. Qualitative data based on laboratory specific normal ranges will be categorized according to the categories "negative/positive".
2. Quantitative results will be categorized qualitatively based on specific normal ranges and presented as qualitative result "normal"/"above normal". The quantitative data for these parameters will be listed.
3. Number and percentages of patients with values considered as clinically significant by the investigator will be tabulated.

Retention samples from safety visit of part I and II and pre-dose samples from part II are only listed. No summaries will be produced.

11.8 Clinical safety laboratory

All safety lab values will be re-calculated to SI units before further processing.

The following statistical analyses will be presented for part I (SAF) and on event level from part II for FBE (separated by ODP/ODT, hospitalization, age group as appropriate) per lab test (as listed subsequently). Note that 'baseline' refers to the pre-dose measurement within each observation period of the indication/event:

1. Quantitative data will be examined for trends using descriptive statistics (number of patients/events with data, number of patients/events with missing values, mean, SD, median, minimum, and maximum) of measured values at baseline and each planned post-baseline visit over time.
2. Qualitative data based on laboratory specific normal ranges will be categorized according to the categories (e.g. below normal/normal/above normal) and presented as number and relative frequency of patients (and/or events).
3. Number and percentages of patients/events with on treatment values considered as clinically significant (CS) by the investigator will be tabulated (across planned visits). Out of range values not assessed for clinical significance are not included in the analysis and are provided in Listing.

Note that in the listings, laboratory values that are outside the normal range will additionally be flagged. Any out-of-range values that are identified by the investigator as being clinically significant will also be shown in an extra data listing. Additionally, a separate listing showing the normal ranges will be generated.

Hematology and clinical chemistry

Hematology tests include RBC, WBC, platelet count, hemoglobin, and hematocrit (all quantitatively).

Biochemistry tests measure aspartate aminotransferase, alanine aminotransferase, γ -glutamyltransferase, alkaline phosphatase, total bilirubin, creatinine, urea, potassium, sodium, calcium, chloride (all quantitatively).

Urinalysis

Blood, leukocytes, protein, glucose, ketones, nitrite, bilirubin, urobilinogen were measured only qualitative, pH was measured quantitative. For the analysis only qualitative results will be used (for pH the normal ranges are used for classification of results into "normal", "abnormal"). Frequencies and percentages of normal and abnormal values will be presented. The quantitative results will only included in the listings.

Markers of coagulation activation

Coagulation activation parameters include PT, PT(INR), aPTT, TAT, F1+2, D-dimer.

Measurements of coagulation activation parameters from additional samplings (beside pre-defined timepoints) taken as required per investigator will be listed and not used in the analyses.

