	
 
Change in clinical laboratory assessments of hematology, biochemistry, and urine analysis
 
	
	
 
Change in markers of coagulation activation: PT(INR), aPTT, TAT, F1+2, D-dimer
 
	

Biostatistical Concept	All data collected will be listed and tabulated. Categorical variables will be presented with absolute and relative frequencies. For continuous variables descriptive statistics will be given including mean, standard deviation, median, quartiles, minimum, and maximum. Additionally, for PK data, efficacy and safety parameters, 95 % confidence intervals will be calculated where appropriate. PK parameters will be summarized by descriptive statistics for each age group, and compared descriptively between age groups. No formal statistical test will be used. All analyses of this open-label study will be performed on intention-to-treat (ITT) as well as per protocol population (PP). ITT population will include all patients who received at least any portion of BT524. The PP population will include all patients who received at least 90% of the planned total dose of BT524, met all inclusion and no exclusion criteria, complied with the protocol procedures and had no major deviations impacting on study analysis.
	Response to therapy with BT524 will be evaluated per bleeding event using a 4-point scale ('none', 'moderate', 'good', 'excellent') by the investigator. The clinical response, summarizing the excellent and good rating, will be analysed descriptively (providing estimate and 95% confidence interval). These estimations will be compared with a historical control from a retrospective physician survey, where the outcome excellent/good was reported with 90%. All analyses will be described in detail within a statistical analysis plan (SAP). The PK of BT524 will be analyzed and reported in a separate report
First Patient In	Adults: 20-Mar-2013
(planned)	Children/Adolescents (≥ 6 to < 18 years): 09-Nov-2014
	Children < 6 years: Q2/2018 (planned)
Last Patient Last Visit (planned)	Q1/2020

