## 14.5.1.3 Coagulation Parameters

The following safety coagulation parameters will be investigated:

• Prothrombin time (PT) / International normalized ratio (INR)

PT is a measure of the integrity of the extrinsic and final common pathways of the procoagulant cascade. PT presents the time for patient plasma to clot after the addition of calcium and thromboplastin as an activator of the extrinsic pathway. Therefore, deficiencies or inhibitors of clotting factors within the extrinsic (factor VII) and final common pathways (factors V, X, II, I [fibrinogen]) result in prolongation of the PT.

The INR is a mathematical conversion of a patient's PT that accounts for the sensitivity of thromboplastin used by factoring in the international sensitivity index (ISI) values supplied by its manufacturer PT (Kamal et al. 2007).

- Activated partial thromboplastin time (aPTT) aPTT measures the integrity of the intrinsic and final common pathways of the coagulation cascade and represents the time for patient plasma to clot after the addition of phospholipid (intrinsic pathway activator) and calcium (Kamal et al, 2007).
- Thrombin-antithrombin III complex (TAT)
   TATs develop during the inactivation of thrombin the central enzyme of the coagulation system via complexion with anti-thrombin. TATs are also an indirect measure of thrombin generation. In combination with F1+2

hypercoagulable status can be detected (Wagner and Dati 2008).

• Prothrombin fragments 1 and 2 (F1+2)

During the activation process of prothrombin to thrombin  $F_{1+2}$  are split off and represent an indirect measure of thrombin generation. They are useful to detect and follow-up hypocoagulable status (Wagner and Dati 2008).

• D-dimer

D-dimer is a fibrin degradation product (or FDP), a small protein fragment present in the blood after a blood clot is degraded by fibrinolysis. D-dimer contains two crosslinked D fragments of the fibrinogen protein. D-dimers are produced when fibrin is cleaved by plasmin. The presence of D-dimer may be used to assist with the diagnosis of DIC, Deep Venous Thrombosis (DVT) or Pulmonary Embolism (PE).

Time points for the assessment of coagulation parameters are given in the study flow charts (see **section 3**). Coagulation parameters are to be determined locally or centrally.

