### 15.2.6 Safety Analysis

Adverse events (AEs) will be coded by means of the MedDRA® dictionary. Incidence rates (i.e. number and percentage of affected patients) will be calculated for the coding levels *system organ class* and *preferred term*. Further analyses of AEs will focus on seriousness, intensity, causal relationship to study medication, and outcome. Serious adverse events (SAEs) will be displayed in detail.

Safety laboratory assessments will be categorized with respect to the laboratory specific reference ranges as normal/abnormal. Abnormal values will be further classified with respect to clinical relevance. Changes over time will be described by means of "shift-tables".

Safety analysis will be based on the safety population.

Descriptive methods will be applied for all variables of safety. Details will be provided in the statistical analysis plan.

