2.1 Changes to the study protocol

The statistical analysis as specified in this SAP is consistent with the statistical analysis as specified in the study protocol (version 6.0).

In the study protocol age groups were defined to describe/define differences in time points of study assessments to be performed for different age groups (see flowchart of study in study protocol section 3). In the SAP age groups were defined differently for data analyses.

Shift tables specified in the study protocol for safety laboratory assessment will be not used.

No changes in the clinical study protocol were considered necessary by the Sponsor to handle clinical protocol deviations possibly related to the COVID-19 pandemic at the end of the study. It was therefore decided in the Blinded Data Review Meeting (BDRM) of June 25, 2020, that any non-conformities in the study conduct caused by the COVID-19 pandemic will be described in a note to file, and any COVID-19 related protocol deviation per patient will be listed in BDRM minutes and presented in study listings where appropriate.

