11.5 Vital signs

Vital signs are measured with the following method/unit:

- Blood pressure [mmHg]
- Heart rate in beats/min measured by pulse rate
- Body temperature in grade Celsius [°C] (tympanic measurements)

Measured values of vital signs will be summarized descriptively across the measurement time points (per observation period, cf. study protocol flowchart section 3) for part I (SAF) and on event level from part II (separated by ODP/ODT, hospitalization, age group) for FBE. Note that 'baseline' refers to the pre-dose measurement within each observation period of the indication/event. A listing with all patients vital signs data will be presented.

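### The SAP drops the laboratory shift tables and plans no change-from-baseline summary for laboratory values, coagulation markers or vital signs, although the protocol names change in each as a safety criterion

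*SAP*

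**What the plan says.** Protocol section 2 (Study Synopsis, secondary criteria, safety) words three items as change: vital signs, laboratory values ("Change in clinical laboratory assessments of hematology, biochemistry, and urine analysis") and coagulation markers ("Change in markers of coagulation activation: PT(INR), aPTT, TAT", followed by F1+2 and D-dimer). For safety laboratory data, protocol 15.2.6 says: "Changes over time will be described by means of" shift tables.

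SAP 2.1 says: "Shift tables specified in the study protocol for safety laboratory assessment will be not used". It gives no reason and names no replacement, and the same section calls the SAP's analysis consistent with the protocol.

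SAP 11.8 plans three outputs for laboratory and coagulation data:

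1. descriptive statistics "of measured values at baseline and each planned post-baseline visit over time";
2. counts below, within and above the laboratory's normal range;
3. counts of values the investigator judged clinically significant. Here "Out of range values not assessed for clinical significance are not included in the analysis"; they are only listed.

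Urinalysis is analysed as normal or abnormal. For vital signs, SAP 11.5 says: "Measured values of vital signs will be summarized descriptively across the measurement time points".

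On laboratory source, protocol 14.5.1.3 says: "Coagulation parameters are to be determined locally or centrally". Haematology, biochemistry and urinalysis are done at the local laboratory only (protocol 14.5.1.5).

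**The concern.** A criterion worded as change needs an analysis that compares each patient, or each event, with its own pre-dose value. For these three data types the SAP removes the one such analysis the protocol had specified and adds none. It does plan change or shift elsewhere: change from baseline for fibrinogen antigen, fibrinogen activity and MCF (SAP 10.1 to 10.3), and shift tables for ECG and physical examination (SAP 11.9, 11.10).

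The coagulation markers carry most of the weight. Protocol 11.7 has F1+2, TAT and D-dimer monitored for signs of hypercoagulability, and thrombosis is an adverse event of special interest. A summary that cannot separate a within-patient rise from a change in who was sampled, or in which laboratory reported, is weak evidence in either direction.

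**Working it through.** The plan states no figure on this point, so there is none to reproduce. The check sets the passages side by side and asks what each retained output can show.

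**1. Criterion against planned output**

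| Data type | Protocol synopsis | Protocol 15.2.6 | SAP text and SAP 15.1 table titles |
|---|---|---|---|
| Safety laboratory | change | shift tables | measured values, normal-range counts, clinical-significance counts; no change or shift |
| Coagulation markers | change | not named separately | as above; no change or shift |
| Vital signs | change | no shift tables | measured values; no change |

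In SAP 15.1, the haematology, chemistry and coagulation tables (14.3.3.1.x, 14.3.3.2.x, 14.3.4.6.x) are titled as descriptive statistics or clinical-significance counts. No table title covers the normal-range counts for these three groups.

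**2. Can marginal counts recover change?**
Inputs: N = 23 planned part I patients (SAP section 3, Table 1), *a* abnormal at baseline, *b* abnormal after dosing. The number newly abnormal lies between max(0, b − a) and min(b, N − a). The counts *a* and *b* are assumed.

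- a = 5, b = 5: from max(0, 0) = 0 to min(5, 18) = 5.
- a = 5, b = 8: from max(0, 3) = 3 to min(8, 18) = 8.

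The same pair of counts therefore fits no new abnormality or five.

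**3. Can visit means recover change?**
If exactly the same patients are measured at both visits, the difference of the means equals the mean change, but the spread of the change is still lost. If the patients differ, even the mean change is lost. Protocol 14.5.1.3 sets the part I coagulation schedule by age. The counts below use two assumed splits of 23 patients (adults / 6 to <18 / 2 to <6 years): A = 10/10/3 and B = 14/6/3. The protocol requires the first 10 patients to be adults, allows patients 11 to 20 to be aged 6 or over, and plans at least 3 children under 6.

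| Time point | Groups scheduled | A | B |
|---|---|---|---|
| Pre-dose | all | 23 | 23 |
| End of infusion | under 2 years | 0 | 0 |
| 1 h | adults; 2 to <6 | 13 | 17 |
| 4 h, 8 h | adults; 6 to <18 | 20 | 20 |
| Day 1 | adults; 6 to <18; infants and toddlers | 20 | 20 |
| Day 2 | adults; 2 to <6 | 13 | 17 |
| Days 4, 10, safety visit | adults | 10 | 14 |
| Days 7, 14 | adults; 6 to <18 | 20 | 20 |

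Under split A the 1 h and 4 h means share only the 10 adults: 3 young children leave and 10 older children enter. Day 4 covers 10 of the 23 patients in the pre-dose mean (14 of 23 under B). Table 14.3.4.6.1 is titled by time point only.

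**4. Laboratory source**
SAP 11.8 converts values to SI units but sets no rule on local versus central results. As an illustration only, assume two laboratories whose scales differ two-fold and whose share of results moves from 50:50 to 40:60. The mean goes from 0.5×1 + 0.5×2 = 1.5 to 0.4×1 + 0.6×2 = 1.6, a rise of 1.6/1.5 − 1 = 6.7% with no patient changing.

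**The case against.** Several points on the other side stand, and they limit the finding.

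- A reader might infer that only raw values are reported. That is true of vital signs but not of laboratory and coagulation data, for which SAP 11.8 adds normal-range and clinical-significance counts.
- A reader might infer that local and central results are pooled throughout. The documents do not say so. The mix is possible only for coagulation markers, and pooling there is inferred from the SAP's silence. Protocol 13.1.1.2 ties the choice to local availability of validated tests, which suggests a site-level choice; nothing shows a patient's laboratory changing between visits.
- A reader might infer that shift tables were removed for all three data types. None were planned for vital signs. Whether those in 15.2.6 covered coagulation markers is unclear, because protocol 14.5.1.5 lists the safety laboratory separately from coagulation.
- The drop is declared openly in SAP 2.1. Protocol 14.5.1 lists the same parameters without the word change, and 15.2.6 leaves details to the SAP.
- A reader might infer that a thrombotic signal would be missed. Clinically relevant abnormal values become adverse events, thromboembolic events have their own tables, ultrasonography is scheduled or triggered, the DMC reviews individual safety data, and all values are listed with out-of-range flags. With about 36 patients those listings can be read.
- SAP 5.1 says age subgroups are generally shown in columns, which could apply to Table 14.3.4.6.1 despite its title. That would confine the problem of changing patients largely to the overall column.
- Protocol 14.5.2 asks for every laboratory result to be evaluated, so ungraded out-of-range values should be few.

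What remains is that none of these provisions summarises change within a patient or event.

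**Conclusion.** The point holds as a gap between a declared criterion and its analysis. The laboratory shift tables are dropped without a reason, and no summary of within-patient change is planned for laboratory values, coagulation markers or vital signs. The gap follows from the documents' text and table titles and needs no assumed number.

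Its effect on the results cannot be sized from the documents. The counts of 5 and 8, the two age splits and the two-fold laboratory difference are assumptions that show the mechanism, not predictions. The age-dependent coagulation schedule is fact; that the overall means mix different patients follows from it, subject to how Table 14.3.4.6.1 is finally laid out.

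This is a weakness in descriptive secondary safety reporting. It should be corrected, chiefly for the coagulation markers, but it does not touch the primary PK objective or the confirmatory MCF test.

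**What to change.** In SAP 11.5 and 11.8 and the matching tables in 15.1:

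1. Add change from pre-dose per patient (part I) and per event (part II), using only patients or events with both values and showing the number of pairs. For coagulation markers, use pairs from the same laboratory source.
2. Restore the baseline-to-post-dose below/normal/above shift tables for safety laboratory values, and extend them to coagulation markers using each laboratory's own reference range. Those ranges are already held for Listings 16.10.5, 16.11.5 and 16.18.5.
3. Optionally, add a count of out-of-range values not assessed for clinical significance.

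Pre-dose coagulation samples are scheduled in every age group, so the pairs exist. Biochemistry and urinalysis in children under 6 have no scheduled pre-dose sample. In part I the screening value can serve as baseline under SAP 5.5; in part II there is usually no pair, and the table should show that.

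The cost is SAP wording, some programming and a few extra table columns. No new data are needed.

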### 14.5.2 Methods for Assessing, Recording and Analyzing Safety Parameter(s)

All laboratory results have to be evaluated in the eCRF according to the following pattern:

- a) outside reference range but not clinically relevant (e.g. due to already known conditions, due to sampling conditions, only marginal deviation, due to underlying diseases in the study population)
- b) outside reference range and clinically relevant.

Laboratory values which are outside the reference range and assessed as clinically relevant have to be controlled and documented as adverse events if they occur for the first time after administration of investigational medicinal product BT524.

If abnormal laboratory values are signs of an adverse event (e.g. an infection) that has already been reported during the present study, this has to be stated but the respective abnormal laboratory value does not constitute a separate adverse event.

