5.1 General statistical methods

All data collected will be analyzed using appropriate statistical methods for the production of all tables, listings and figures and for the statistical analysis.

Data will be summarized with respect to demographic and baseline characteristics, efficacy and safety observations and measurements (cf. section 4). Tabulations will be presented for each parameter. Generally, age subgroups will be presented in columns and overall totals will be provided, too. Data will be presented for the overall population, and for ODP and ODT, each for minor events, major events and overall in rows, as specified in the section for the respective parameter.

For continuous variables descriptive statistics will be given including mean, SD, median, quartiles, minimum, and maximum. Additionally, for PK data, efficacy and safety parameters 95 % confidence intervals will be calculated where appropriate. Categorical data will be presented in frequency tables using counts and percentages. In addition, the number of patients with missing values will be displayed. Percentages relate to the number of patients (or events, for part II) with data. This includes data obtained by the respective missing data replacement strategy (see section 5.3 Missing data).

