5.3 Missing data

5.3.1 Missing severity assessment for adverse events

If severity is missing for an AE starting prior to the administration of IMP, then a severity of “Mild” will be assigned. If the severity is missing for an AE starting on or after administration of IMP, then a severity of “Severe” will be assigned. The imputed values for severity assessment will be used for incidence summaries, while the actual values will be used in data listings.

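### SAP 11.8 keeps ungraded out-of-range laboratory values out of the clinically significant tables, so those counts are lower bounds, and no listed table shows how many values were left ungraded

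*SAP*

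**What the plan says.** SAP section 11.8 plans three laboratory summaries.

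- Item 1 gives descriptive statistics of the measured values at baseline and each planned later visit.
- Item 2 sorts results into range categories such as below, within or above normal and gives their frequencies. It sets no condition about grading.
- Item 3 counts patients or events with on-treatment values that the investigator considered CS, and ends with the rule at issue: "Out of range values not assessed for clinical significance are not included in the analysis and are provided in Listing".

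The section then adds: "Note that in the listings, laboratory values that are outside the normal range will additionally be flagged".

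The protocol expects grades to exist. Section 14.5.2 says: "All laboratory results have to be evaluated in the eCRF according to the following pattern". The pattern has two classes, out of range but not clinically relevant, and out of range and clinically relevant. Section 15.2.6 says of the analysis: "Abnormal values will be further classified with respect to clinical relevance".

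Two other SAP rules bear on the point. Section 5.1 sets the denominator: "Percentages relate to the number of patients (or events, for part II) with data". It also says that numbers with missing values will be displayed. Section 5.3 covers missing investigator judgements on adverse events (AEs). "If the severity is missing for an AE starting on or after administration of IMP", it is counted as severe; a missing relationship is counted as related, and missing seriousness as serious.

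**The concern.** The SAP provides for ungraded abnormal values, which the protocol does not allow for, and resolves them in the favourable direction. In the CS count, such a patient is treated the same as one whose values were all normal or were graded not relevant. For AEs, section 5.3 resolves a missing judgement the other way.

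The AE tables do not make up for this. Under protocol section 14.5.2 an out-of-range value becomes an AE once it is assessed as clinically relevant and is new after BT524. An ungraded value may not trigger that step, and section 5.3 then has no AE record to act on.

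The samples are small, so a few ungraded values can move a percentage noticeably. The coagulation markers matter because protocol section 11.7 says F1+2, TAT and D-dimer are monitored to detect hypercoagulability, and thrombosis or thromboembolism is an AE of special interest in section 14.6.1.

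**Working it through.** The plan states no figure for this rule, so there is nothing to reproduce. The check is a set of bounds for one test at one time point, with one value per patient.

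**Inputs**

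- n = patients with a value. Part I plans 23 patients (SAP section 3, Table 1); fewer will have a value at time points where children under 6 years are not sampled.
- c = patients rated CS. Assumed.
- u = patients whose value is out of range and ungraded. Not in the documents; assumed to be 1 to 4.

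**Formulas**

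- Count shown under item 3: c. Possible true count: c to c + u.
- Percentage shown if ungraded patients stay in the denominator: c / n.
- Percentage shown if they leave it: c / (n − u).
- Upper bound: (c + u) / n.

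**Results for n = 23**

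| c | u | Kept in denominator | Dropped | Upper bound |
|---|---|---|---|---|
| 0 | 1 | 0/23 = 0.0% | 0/22 = 0.0% | 1/23 = 4.3% |
| 0 | 2 | 0/23 = 0.0% | 0/21 = 0.0% | 2/23 = 8.7% |
| 0 | 4 | 0/23 = 0.0% | 0/19 = 0.0% | 4/23 = 17.4% |
| 2 | 2 | 2/23 = 8.7% | 2/21 = 9.5% | 4/23 = 17.4% |
| 2 | 4 | 2/23 = 8.7% | 2/19 = 10.5% | 6/23 = 26.1% |

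The count shown is the minimum in every row. The percentage is the minimum c / n only if ungraded patients are kept or c = 0. If they are dropped it sits slightly above that floor.

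**Why the percentage still tends to be low when they are dropped.** Only out-of-range values leave, while in-range values stay. Take n = 20: 10 in range, 6 out of range and graded with 2 of them CS, and 4 out of range and ungraded. Suppose the ungraded values are CS as often as the graded out-of-range ones (2/6).

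- Expected CS patients: 2 + 4 × 2/6 = 3.33, or 3.33/20 = 16.7%.
- Shown: 2/20 = 10.0% if kept, 2/16 = 12.5% if dropped.
- Upper bound: 6/20 = 30.0%.

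If none of the four were truly CS, the true figure would be 10.0% and the dropped version would overstate it slightly. The direction therefore rests on the ungraded values being CS more often than c / (n − u).

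**Where the ungraded values do appear.** Items 1 and 2 and the listings do not depend on grading. In Appendix 15.1, the table titles for haematology, chemistry and coagulation name only descriptive statistics or CS frequencies, and none names range categories. SAP section 2.1 drops the laboratory shift tables.

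**The case against.** The strongest reply is that little is hidden. The exclusion stands inside item 3 and governs only the CS tabulation. A reader might infer that ungraded abnormal values are removed from the laboratory analysis or reach no frequency table. The documents do not support that: item 1 keeps them in the summary statistics, item 2 counts them by range category, and the listings flag them.

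The absence of an Appendix 15.1 title for range categories is weak evidence. The urinalysis tables are also titled as descriptive statistics, yet section 11.8 says they show normal and abnormal frequencies, and layouts sit in a separate shells document. Item 2 does speak of qualitative data while haematology and biochemistry are described as quantitative, so its scope for those panels is unclear, but unclear is not absent.

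Section 5.1 may also cause ungraded values to be shown as missing. That is possible, but item 3 has its own rule and does not say so.

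The number of ungraded values may be zero. Protocol section 14.5.2 requires grading, and section 16.1 has queries repeated until solved. This limits the size of the effect but does not make the rule neutral.

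Finally, the AE analogy is imperfect. An AE has already been judged unfavourable, whereas an out-of-range value has not. Protocol section 14.5.2 names underlying disease in the study population as a reason for non-relevance, and section 14.5.1.3 says that fibrinogen deficiency prolongs the prothrombin time. Counting every ungraded abnormal value as CS could create false signals. This part stands and argues against making a worst-case count mandatory.

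**Conclusion.** The point holds for the CS tables. Under item 3 the CS count is a lower bound whatever the data, and the CS percentage is biased low by an amount that depends on the number of ungraded values. That number is unknown, and the effect is zero if grading was complete. The percentages above illustrate the bounds and do not estimate this trial's result.

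Three stronger readings are not supported:

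- That the percentage is always the best case. This is exact only if ungraded patients stay in the denominator or c = 0, and section 5.1 does not say whether an ungraded value counts as data.
- That the CS tables are the main laboratory and coagulation safety result. The SAP gives them no such rank, and clinically relevant new abnormalities also go to the AE tables.
- That coagulation markers are most exposed because a central laboratory may measure them. The documents do not say who grades central results.

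Neither the primary pharmacokinetic objective nor the confirmatory clot-firmness test is affected. The change is worth making because it is nearly free and removes a one-sided rule from a safety table.

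**What to change.** Replace the last sentence on ungraded values in SAP section 11.8, item 3, by: *Out-of-range values without an assessment of clinical significance are shown as a separate row (out of range, not assessed) in each clinically significant table; the denominator is all patients/events with a value for that test and time point.*

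SAP section 11.6 already uses a missing or not-done category for inhibitory antibodies, so the format has a precedent. If all values were graded, the row shows zeros and documents completeness.

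A row counting ungraded values as CS should not be mandatory. If it is given, it should be an optional sensitivity bound labelled as an upper limit, because disease-related abnormal coagulation values are expected in these patients.

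The cost is one sentence and one table row. The laboratory figures may look slightly less favourable.
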